#### **Document maintenance**

The MSK PI and the MSK Alliance Site PI will maintain adequate and accurate records to enable the implementation of the protocol to be fully documented and the data to be subsequently verified.

A regulatory binder for each MSK Alliance site will be maintained onsite at the MSK Alliance site. An electronic regulatory binder will also be maintained at MSK.

After study closure, the participating site will maintain all source documents, study related documents and CRFs for 3 years.

### **Noncompliance**

If a MSK Alliance site is noncompliant with the protocol document, accrual privileges may be suspended and/or contract payments may be withheld (if applicable), until the outstanding issues have been resolved.

## **14.1 PROTECTION OF HUMAN SUBJECTS**

We aim to protect the rights of the participants with a comprehensive informed consent procedure. A printed consent form and letter of invitation will be provided to all participants (including primary care providers). The PIs and RSA will be available to respond to questions or concerns of the participants. Individuals will be informed that participation is voluntary. The purpose of the study and potential risks and benefits will be explained during the informed consent process. All potential patients will be informed as to their rights as volunteers in a research study. The right to refuse or withdraw at any point during the study, without compromising medical and other care will be explained. The purpose of the study and potential risks and benefits associated with it will be stated.

Risks for this study are minimal, and we will aim to protect participants from risk. Participants will complete the consent form and respond to the study surveys and interviews. The information presented to survivors about their symptoms may cause psychological distress. We have taken steps to minimize the risk of distress attributable to study participation. All study personnel will be trained and supervised to implement study procedures. All assessments will be conducted by research staff skilled in interviewing participants in a sensible manner with the utmost respect for human subjects" issues. In the unlikely event of psychological distress observed or expressed by participants, appropriate referrals will be made. Participants will be treated with respect and sensitivity.

There are no anticipated toxicities or side effects from this nontherapeutic study. We do not anticipate any serious adverse events needing to be reported. However, a patient could experience severe anxiety, for example, when reporting any current symptoms. If such an SAE occurs, we will report it as described in section 14.2 below.

As an alternative to participation, any patient may choose not to participate or to terminate participation at any time. The patient would then receive usual care in the survivorship clinic. Participation is completely voluntary. We will inform patients of this during the informed consent process.

Participants may benefit from this study. The NP will receive an Interactive Discussion Guide summarizing medical history, relevant symptoms, and recommendations for care (including symptom management, routine oncologic follow-up, and recommended preventive care). This may help the NP and survivor focus on the most salient issues while promoting the survivor's involvement in his or her care. This may also serve to ensure adherence to current guidelines and promote standardized care for survivors. After the visit, the cancer survivors will receive a Survivorship Care Plan with a plain-language treatment summary and personalized recommendations for ongoing care, which may help the survivors, their primary care providers, and oncology providers plan ongoing management strategies. In Aim 1: Part 2, participants' primary care providers will also receive a Survivorship Care Plan. In addition, survivors will have the opportunity to report their symptoms, engaging the patient in their survivorship care. Further, for the NP who is tasked with providing Survivorship Care Plans as part of routine care in the survivorship clinic, HN-STAR alleviates or minimizes the burden of manual data entry. For primary care providers, they will receive personalized information to help guide the ongoing care of their patients who completed treatment for head and neck cancer.

Another benefit is the knowledge gained from the study. Following curative therapy, head and neck cancer survivors can face significant challenges that impact both quality of life and overall survival. HN-STAR may improve our ability to address oncologic and non-oncologic issues – including surveillance for recurrence, management of late effects of therapy, screening for second cancer, and prevention and treatment of co-morbid illness – during routine survivorship care. This study will evaluate if HN-STAR is feasible in actual practice, if it improves the care provided during the clinical encounter, and if the resulting Survivorship Care Plan is useful to stakeholders. Results from this study will provide critical feedback for modifying HN-STAR and implementing and evaluating it as an intervention in a future multi-center trial.

There will be no financial costs or burdens to the participants. For those participants in Aim 1: Part 1, who are asked to arrive for their clinic visit one hour early and stay 30 minutes after, and who drive to their visit will receive payment for parking as an incentive to participate.

Confidentiality will be maintained at all times during the study administration. The WebCore platform has been reviewed by the MSKCC Information Security Department and conforms to current MSK and HIPAA standards for the protection of PHI. Participant interviews will take place in a private clinic room. Participants will be informed that information collected during their participation in this study is considered confidential. All data gathered will be kept in a secured location. Confidentiality of each participant's data will be protected with utmost care. Participants will specifically not be identified in manuscripts or public presentations.

## **14.2 Privacy**

MSK's Privacy Office may allow the use and disclosure of protected health information pursuant to a completed and signed Research Authorization form. The use and disclosure of protected health information will be limited to the individuals described in the Research Authorization form. A Research Authorization form must be completed by the Principal Investigator and approved by the IRB and Privacy Board (IRB/PB).

## **14.3 Serious Adverse Event (SAE) Reporting**

It is not anticipated that any SAEs will result from the processes described in this protocol (i.e., related to completing online assessments and interviews). A hypothetical example, albeit unlikely,

might be severe anxiety or distress as a result of the completing the surveys. Although it will be the responsibility of the investigators to report any such SAE resulting from processes described in this protocol, it will not be their responsibility to report serious adverse events related to treatments or underlying disease in patients who are participating in this study. Patients enrolled in this study may be receiving treatments for cancer late effects or other conditions, but these treatments are not directed or provided by the research described in this protocol, and are at the discretion of clinical staff separate from the investigators on this study. Adverse events related to those interventions should be managed by the clinical staff as a part of standard care, via routine approaches.

An adverse event is considered serious if it results in ANY of the following outcomes:

- Death
- A life-threatening adverse event
- An adverse event that results in inpatient hospitalization or prolongation of existing hospitalization
- A persistent or significant incapacity or substantial disruption of the ability to conduct normal life functions
- A congenital anomaly/birth defect
- Important Medical Events (IME) that may not result in death, be life threatening, or require hospitalization may be considered serious when, based upon medical judgment, they may jeopardize the patient or subject and may require medical or surgical intervention to prevent one of the outcomes listed in this definition

Note: Hospital admission for a planned procedure/disease treatment is not considered an SAE.

SAE reporting is required as soon as the participant signs consent. SAE reporting is required for 30-days after the participant's last investigational treatment or intervention. Any events that occur after the 30-day period and that are at least possibly related to protocol treatment must be reported.

If an SAE requires submission to the IRB office per IRB SOP RR-408 „Reporting of Serious Adverse Events”, the SAE report must be sent to the IRB within 5 calendar days of the event. The IRB requires a Clinical Research Database (CRDB) SAE report be submitted electronically to the SAE Office as follows:

For IND/IDE trials: Reports that include a Grade 5 SAE should be sent to [[contact]](mailto:[contact]). All other reports should be sent to [[contact]](mailto:[contact]).

For all other trials: Reports that include a Grade 5 SAE should be sent to [[contact]](mailto:[contact]). All other reports should be sent to [[contact]](mailto:[contact]).

The report should contain the following information:

Fields populated from CRDB:

- Subject's initials
- Medical record number

- Disease/histology (if applicable)
- Protocol number and title

Data needing to be entered:

- The date the adverse event occurred
- The adverse event
- The grade of the event
- Relationship of the adverse event to the treatment (drug, device, or intervention)
- If the AE was expected
- The severity of the AE
- The intervention
- Detailed text that includes the following
  - A explanation of how the AE was handled
  - A description of the subject's condition
  - Indication if the subject remains on the study
- If an amendment will need to be made to the protocol and/or consent form
- If the SAE is an Unanticipated Problem

The PI's signature and the date it was signed are required on the completed report.

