## **4.1 OVERVIEW OF STUDY DESIGN/INTERVENTION**

### **4.2 Design**

This is a pilot study of HN-STAR for routine follow-up visits in two survivorship clinics – the Head and Neck Survivorship Clinic at MSK and the Survivorship Clinic of the Gray Cancer Center.

Patient Survivorship Program at HH. Each clinic is led by a single NP, [name] at MSK (co-Investigator) and an NP at HH, [name], who is a co-investigator on the HH study team. Each hospital has determined patient eligibility for the clinic. The head and neck survivors seen in each clinic have completed treatment for head and neck cancer at least one year prior and have no evidence of disease. In standard care, the NP provides oncologic follow-up, creates and delivers a survivorship care plan, addresses healthy behaviors, and ensures that the survivor has a primary care provider who will manage general preventive care.

For this pilot study, we will incorporate HN-STAR into a routine NP-led survivorship visit, in order to assess feasibility of HN-STAR in clinical practice. For a single routine visit, each patient will report his or her medical history, preventive care, and symptoms online, and this information (as well as other medical history information) will populate an Interactive Discussion Guide for the NP to use in the clinic visit. In Aim 1: Part 2 of the study, each patient and his or her primary care provider (PCP) will receive the automatically generated Survivorship Care Plan. This study will use surveys at multiple time points during this process to elicit usability and feasibility data from patients, NPs, and PCPs regarding the use of this system (Aim 1).

This study also includes non-survey outcomes assessments. HN-STAR will automatically collect patient reports about symptoms, preventive care, and medical history. Other oncology-related outcomes (such as referrals, medications, and other treatment decisions) will appear in the clinic note for each visit. Both data sources will be used to establish baseline measures and inform feasibility of collecting data for a future trial (Aim 2). In addition, as part of Aim 2, the oncology-related metrics from the clinic visit will enable us to gain preliminary insight into changes after HN-STAR, using a pretest-posttest design.

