**Physical exam**

- Assess for increased neck size or obesity indicating possible causes of sleep apnea

**Recommendations for evaluation and management** (Check all that apply.)

- Referral to primary care provider
- Sleep log
- Sleep hygiene review (routine of bed time and awakening, light exposure, avoiding naps, and only being in bed to sleep)
- Consider discontinuing or reducing use of steroids, opioids, anti-depressants.
- Physical activity (moderate aerobic exercise for 2.5 hours a week and strength training 2-3 days a week)
- Referral to psychology (MSK)
- Referral to psychology (outside)
- Referral to integrative medicine (MSK)
- Prescription for sleep aide
- Patient education material on sleep
- Video on sleep
- Not discussed because chronic and previously addressed
- Other (Note names of providers or other details not described above)

**4.2.4** Finally, the **Survivorship Care Plan** will present a treatment summary and plan of care. HN-STAR generates a Survivorship Care Plan after each visit (See template in Appendix C). The treatment summary contains a plain-language cancer history. The plan of care contains personalized recommendations for cancer surveillance, management of late effects, and preventive care. It also reports a list of non-cancer conditions reported by the patient. Each recommendation includes a schedule and clear delineation of who is responsible. The plan of care also contains generic survivorship information, with a description of signs and symptoms to report to the oncology provider, contact information for the oncology provider, and recommendations to visit a primary care provider.

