#### **4.2.5 Clinical flow using HN-STAR**

1. *Before the survivorship visit:* At MSK, the institutional database of CPT codes will automatically populate the Automated Treatment Checklist in HN-STAR, and the NP will verify its accuracy. At HH, the NP will complete the Manual Treatment Checklist. At both sites, the Treatment Checklist will inform treatment-based recommendations in the Interactive Discussion Guide and generate a plain-language treatment summary for the Survivorship Care Plan.
2. *Before the survivorship visit,* survivors will complete the online Survivor Self-Assessment. Using the Survivor Self-Assessment and Treatment Checklist data, HN-STAR will create the Interactive Discussion Guide for the clinic visit that presents 1) an oncologic surveillance schedule, 2) a list of severity-based symptom management options, and 3) personalized preventive care and screening recommendations.
3. *During the visit,* the NP will use the Interactive Discussion Guide to facilitate conversation. Specifically, the NP and survivor will discuss ongoing care, select plans for symptom management, and identify who is responsible for each action (NP, survivor, or primary care provider).
4. *At the end of the visit,* the Treatment Checklist will be combined with the selected plan of care from the visit in the Survivorship Care Plan. At the end of the visit, the Survivorship Care Plan will be given to the survivor and discussed with the survivor. For Aim 1: Part 2, after the visit, the Survivorship Care Plan will be sent to each survivor's primary care provider.

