## 11.0 BIOSTATISTICS

**11.1 Sample size.** This feasibility study is not powered to test formal hypotheses. Instead, it will provide feedback regarding the HN-STAR process. We will enroll 10 patients in Aim 1: Part 1. In Aim 1: Part 2, we will enroll 45 additional patients: 30 from MSK and 15 from HH. The MSK clinic sees over 20 patients per month, ensuring that enrollment is attainable. The HH clinic sees approximately 8 patients per month. We anticipate that enrolling 45 patients will not take longer than 6 months. Enrolling PCPs may be more difficult; we anticipate that not all 45 PCPs will complete the Primary Care Provider Survey. Part of our feasibility study is to test whether this method of recruitment and level of incentives will be adequate to recruit PCPs in a future study, and the level of participation will inform this feasibility outcome. Both NPs are integrally involved in implementing HN-STAR in their clinics.

### 11.2 Analysis Aim 1: Parts 1 and 2

The structured survey questions (asked of survivors, NPs, and PCPs in Aim 1: Parts 1 and 2) will be summarized using descriptive statistics. Quantitative outcomes will include survivors' rates of completion of the self-assessment, survey completion rates for survivor, NP, and Primary Care Provider Surveys in the feasibility study. The number of questions to answer is different between surveys and even between respondents, based on skip patterns built into the electronic survey platform. Each survey will be considered complete if at least 75% of questions that are asked are answered. WebCore will automatically capture the percentage of questions that are answered for each survey administered. We will also look at survivor responses by race and ethnicity. Other quantitative outcomes include the median time survivors required to complete the self-assessment, the accuracy of the automated treatment summary (verified against the EMR), the time required for NP verification of the treatment summary, and the length of HN-STAR visits.

Each component of HN-STAR will be evaluated individually for feasibility. We will consider the Survivor Self-Assessment feasible for subsequent effectiveness testing if the following criteria are met:

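### The SAE exemption in Section 14.3 assumes treating staff are separate from the investigators; this is untrue of the NPs who choose visit actions through HN-STAR, and the exemption conflicts with the other SAE clauses

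*Combined protocol and SAP*

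**What the plan says.** Section 14.3 (listed as 14.2 in the table of contents) confines the investigators' duty to SAEs arising from the protocol's own processes, which it explains as online assessments and interviews. Beyond that, "it will not be their responsibility to report serious adverse events related to treatments or underlying disease in patients" taking part. Two grounds are given: "these treatments are not directed or provided by the research described in this protocol", and the treatments "are at the discretion of clinical staff separate from the investigators on this study".

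Other sections describe who treats and how:

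- Section 4.2 (Design): one NP leads each clinic. The MSK NP is labelled a co-investigator, and the Hartford HealthCare (HH) NP is someone "who is a co-investigator on the HH study team". Section 11.1 adds that both are closely involved in putting HN-STAR into their clinics.
- Section 4.2.5 (Clinical flow): during the visit "the NP and survivor will discuss ongoing care, select plans for symptom management, and identify who is responsible for each action".
- Section 4.2.3: the plans chosen are entered into HN-STAR and fill in the Survivorship Care Plan.
- Figure 3 (insomnia excerpt of the Interactive Discussion Guide): the tick-box options include "Consider discontinuing or reducing use of steroids, opioids, anti-depressants", a prescription, several referrals and a free-text entry.

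The remaining SAE text is broader. Section 14.3 also asks for SAE reporting from consent until 30 days after the last study treatment or intervention, and after that for events at least possibly related to protocol treatment. The subsection on Alliance sites makes them send all SAEs to the MSK principal investigator within 3 calendar days. The subsection on MSK's responsibilities speaks of unexpected SAEs at least possibly related to the study intervention.

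**The concern.** A reporting rule should rest on a true description of the study. Here one of its two stated reasons is wrong for the care most closely tied to the tool: the clinician choosing management at the study visit is an investigator, and the choice is made in the study software. The explanation of study processes also omits the two HN-STAR components that carry management recommendations.

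At stake is whether a serious event that may have followed from a guide-selected action is captured. Staff applying the exemption would treat it as routine care and not report it; staff applying the neighbouring clauses would report it. A later statement about SAEs in this study would then depend partly on which sentence each site followed. This matters because Section 14.1 says the study will look at "if it improves the care provided during the clinical encounter", and because visit actions such as referrals and prescriptions are abstracted in Aim 2 (45 Part 2 patients) as metrics before and after HN-STAR.

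**Working it through.** This is a text check. The plan has no figure to reproduce (Section 11.1: "This feasibility study is not powered to test formal hypotheses"), and the only arithmetic is a patient count.

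**1. Who chooses the action?** Section 14.3 says staff separate from the investigators. Section 4.2 says a single NP leads each clinic and both NPs are co-investigators. Sections 4.2.3 and 4.2.5 say that NP, with the survivor, selects the plan. For actions selected at the visit, the premise of separateness is contradicted at both sites.

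**2. Does the research direct or provide the action?** This is less clear-cut. The protocol summary defines the intervention as patients and NPs using HN-STAR to produce a discussion guide and then a care plan, and Section 4.2.3 says the study team developed the symptom recommendations. Against that, the summary gives the treatment plan as none, and no action is mandated. The second ground is doubtful for guide-selected actions, but the text does not refute it.

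**3. What counts as a study process?** Section 4.3 says HN-STAR has four components: Survivor Self-Assessment, Treatment Checklist, Interactive Discussion Guide and Survivorship Care Plan. The explanation in Section 14.3 reaches the assessments and the interviews. It does not reach the Guide or the Care Plan.

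**4. One event under each clause.** Take an SAE within 30 days of the study visit, possibly related to an action newly ticked in the Guide.

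| Text | Result for this event |
|---|---|
| Exemption in 14.3 | Related to a treatment, so investigators need not report it |
| 30-day clause in 14.3 | Reportable |
| After-30-days clause in 14.3, had it occurred later | Depends on whether a guide action is protocol treatment, which is undefined in a study whose treatment plan is none |
| Alliance-site subsection | Sent to the MSK principal investigator within 3 calendar days, whatever the cause |
| MSK responsibilities | If unexpected, passed to the Alliance sites, but only once the MSK IRB has stamped a report; this creates no duty to report in the first place |

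Nothing says which text prevails. Submission to the IRB also depends on an institutional procedure (RR-408) that is not among the documents.

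**5. How many patients fall under each rule?** From Sections 2.0 and 11.1:

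- MSK: 10 (Part 1) + 30 (Part 2) = 40
- HH: 15 (Part 2)
- Total: 40 + 15 = 55, so MSK holds 40/55 = 73% and HH 15/55 = 27%

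The all-SAE rule binds Alliance sites only. HH is the only other clinical site, but the text does not call it an Alliance site. If it is one, 15 patients are under the all-SAE rule and 40 are under Section 14.3 with its exemption.

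**The case against.** The strongest reply is that the misstatement is a slip with little effect. Treatment is routine care: the plan assigns no treatment, the NP already provides follow-up and a care plan in standard practice, and the Guide is an aid that allows a free-text entry or no discussion of a chronic problem. The study is described as minimal-risk and nontherapeutic. The other SAE clauses would bring many such events in anyway.

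Much of this stands, and it rules out several stronger readings that a reader might infer:

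- *Harm from HN-STAR-prompted actions is never reported.* Not supported. The 30-day clause, the possibly-related clause and the Alliance-site rule all point the other way. They conflict with the exemption; they are not cancelled by it.
- *Because investigators conduct all 55 visits, no treatment is given by separate staff.* Not supported. Section 4.2.5 allows responsibility to fall to the NP, the survivor or the primary care provider, and Figure 3 lists referrals. Later treatment by primary care or referral providers may still fit the separate-staff wording.
- *Recommended actions last six months.* Section 7.2.6 schedules an adherence interview at six months and gives no duration for any action.
- *Missed SAEs would distort the decision to move to a randomised trial.* No feasibility criterion in Section 11.2 uses SAEs, and Section 11.4 ties progression to feasibility.
- *Benefit and harm are attributed by opposite rules.* Aim 2 is descriptive, and its definition of an addressed late effect includes explicitly noted inaction.

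What the reply does not remove is the false premise, the omission of the Guide and the Care Plan, and the lack of any order of precedence among the clauses.

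**Conclusion.** The point holds as an internal contradiction in safety-reporting scope. For actions selected at the study visit, the statement that treating staff are separate from the investigators is wrong at both sites, and the exemption built partly on it conflicts with neighbouring SAE text. SAEs possibly related to guide-selected actions may go unreported. They may also be handled differently at MSK (40 of 55 patients) and HH (15 of 55).

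The difference between sites assumes that HH is an Alliance site. The rest does not depend on that. How many events are affected cannot be estimated, because the documents give no SAE rate and no count of guide-selected actions. The medication examples come from one excerpt of the Guide; they show what kind of option the tool presents, and no view is taken on any of them.

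**What to change.** In Section 14.3:

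1. Remove or correct the statement that treating staff are separate from the investigators, so that it agrees with Section 4.2.
2. State that SAEs at least possibly related to use of HN-STAR are reportable at both sites, including those possibly related to an action newly selected in the Interactive Discussion Guide at the study visit.
3. Keep the exclusion for underlying disease and for treatment not selected through the Guide.
4. Reconcile the section with its own 30-day and possibly-related clauses and with the subsections on Alliance sites and MSK's responsibilities. Say whether HH is an Alliance site, what protocol treatment means here, and who judges relatedness when the treating NP is an investigator.

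Making everything listed in the Survivorship Care Plan reportable would go too far, since the plan also carries surveillance and routine preventive care. A question added to the six-month interview could not replace the rule, because that interview exists only in Part 2 and would miss the 10 Part 1 patients.

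The cost is protocol wording, a few extra relatedness judgements and possibly a few extra reports. Design, sample size and analysis do not change.
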